10.2 Secondary Efficacy Variable Analysis

The secondary efficacy endpoints are the following:

- Proportion of subjects free from respiratory failure as defined by free from supplemental oxygen requirement (invasive mechanical ventilation, non-invasive ventilation, high-flow oxygen, or ECMO, CPAP, BiPAP, nasal cannula) at Days 14, 28 and Day 60* Proportion of subjects with mechanical ventilation /intubation at Days 7, 14, 28 and Day 60*
- Change from baseline in clinical status using NIAID 8-point scale and discharge record at Days 7, 14, 28 and 60* Proportion of subjects with at least a one-point improvement in clinical status using the NIAID 8-point ordinal scale and discharge record at Day 14, 28 and 60*
- All-cause mortality at Days 28 and Day 60* Proportion of the subjects discharged from hospital at Day 7, 14, 28 and 60*
- Change from baseline in migration inhibitory factor (MIF), (interleukin 1-beta (IL-1 β), interleukin 6 (IL-6), tumor necrosis factor (TNF- α), and C-reactive protein (CRP) at Day 3, 5, 7 and 14

*Intubated subjects only on Study Day 60

All secondary endpoints that are defined as proportion variables will be analyzed using Pearson's chi-square tests. Secondary endpoints that are defined as the change from baseline will be analyzed using analysis of covariance (ANCOVA) models with treatment group as a factor and the baseline value of the corresponding endpoint as a covariate. All secondary analyses will be conducted using one-sided tests at the alpha=0.025 level of significance, with no adjustments for multiplicity.

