1 INTRODUCTION

This Statistical Analysis Plan (SAP) describes the planned analysis and reporting MediciNova Inc. protocol MN-166-COVID-19-201, *A Randomized, Double-Blind, Placebo-Controlled, Parallel Group Study to Evaluate the Efficacy, Safety, Tolerability, Biomarkers and PK of ibudilast (MN-166) in COVID-19 Participants at Risk for Developing Acute Respiratory Distress Syndrome.*

This phase 2 study is being completed to assess the safety, tolerability, and efficacy of MN-166 in male and female subjects 18 to 80 years of age, inclusive, who are hospitalized for complications from COVID-19 infection, are at risk for developing ARDS, and receive standard of care including anticoagulation. The following documents were reviewed in preparation of this SAP:

- Clinical Study Protocol MN-166-COVID-19-201, amendment 2 issued 01 November 2021 and amendment 4 issued 31 March 2021*
- Case report forms (CRFs) for Protocol MN-166-COVID-19-201.
- ICH E9: Guidance on Statistical Principles for Clinical Trials.
- ICH E3: Guideline for the format and content of the clinical and statistical sections of an application
- ICH E14: Clinical evaluation of QT/QTc interval prolongation and proarrhythmic potential for non-antiarrhythmic drugs

The SAP supplements the clinical protocol. Please refer to the clinical protocol for details on the rationale for the intervention, eligibility criteria, conduct of the trial, clinical assessments and the timing of their use in the trial, definitions and reporting of adverse events, data management conventions, and regulatory oversight and compliance procedures. In case of discrepancies between the SAP and the clinical protocol concerning matters of data analysis, the SAP is authoritative. On all other matters, the clinical protocol is authoritative.

**No subjects were consented under Protocol v.1.0, Amendment 1, and Amendment 3 because they were not submitted to the institutions' IRB.*

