2.2.2 Secondary Outcome Variable(s)

- Proportion of subjects free from respiratory failure as defined by free from supplemental oxygen requirement (invasive mechanical ventilation, non-invasive ventilation, high-flow oxygen, or ECMO, CPAP, BiPAP, nasal cannula) at Days 14, 28 and Day 60*
- Proportion of subjects with mechanical ventilation /intubation at Days 7, 14, 28 and Day 60*
- Changes from baseline in clinical status using the NIAID 8-point ordinal scale and discharged record at Days 7, 14, 28 and 60*
- Proportion of subjects with at least a one-point improvement in clinical status using the NIAID 8-point ordinal scale and discharge record at Days 14, 28 and 60*
- All-cause mortality at Days 28 and Day 60*
- Proportion of the subjects discharged from hospital at Days 7, 14, 28 and 60*
- Change from baseline in migration inhibitory factor (MIF), (interleukin 1-beta (IL-1 β), interleukin 6 (IL-6), tumor necrosis factor (TNF- α), and C-reactive protein (CRP) at Day 3,5,7 and 14
- Incidence, frequency, and severity of adverse events at Day 7, 14, 28 and Day 60*
- Change from baseline of the following parameters at Days 7, 14 and Day 60*:
 - o ALT
 - o AST

Confidential

- o Serum creatinine
- o BUN
- o Complete blood count
- o Total bilirubin
- o D-dimer
- PK plasma concentrations and parameter (PK population)

*Intubated subjects only on Study Day 60

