3 STUDY METHODS AND ENDPOINTS

3.1 Overall Study Design and Plan

This is a randomized (1:1), placebo-controlled, double-blind, parallel-group study of MN-166 (ibudilast) in hospitalized COVID-19 subjects at risk for developing ARDS receiving standard of care including anticoagulation. Approximately 40 participants are planned to be enrolled. The study will consist of a Screening Phase followed by a 7-days Double-blind Treatment (DBT) and Follow-up Phase. Following the Screening Phase, if the subject meets eligibility criteria, subject will be administered treatment with MN-166 (ibudilast) or placebo. Subjects will receive ibudilast 100 mg/d (50 mg b.i.d) or placebo every day for 7 days. The Follow-up phase is consisted of three visits: Day 14, Day 28, and Day 60 (subjects enrolled under amendment 4 only) post-baseline visit.

Subjects who are discharged prior to Day 7 will be given the remainder of their study medication to be taken at home and a pulse oximeter supplied by the sponsor to measure their O₂ levels once daily until Study Day 14.

Eligible participants will consist of males and females ranging in age from 21 to 80 years old, inclusive, who have SARS-CoV-2 infection confirmed by WHO criteria, chest abnormalities consistent with COVID-19 pneumonia, SpO₂ ≤92% on room air, ≥24 BPM, and/or requirement of supplemental O₂.

Overall study design and plan is described in detail in Protocol Section 11.

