13.2 Schedule of Assessments (Amendment 4)

Phase	Screening	Double-Blind Treatment Phase ^{e,g}							Follow-up		
		Day 1 BL	Day 2	Day 3	Day 4	Day 5	Day 6	Day 7	Day 14 ^c (± 3)	Day 28 (±3)	Day 60 (±7)
Study Day	Day -3										
Informed consent	X										
Inclusion/exclusion criteria review	X										
Brief physical exam	X	X		X		X		X	X		
Clinical status using NIAID scale	X	X	X	X	X	X	X	X	X	X	X
Vital signs (BP, RR, HR, Temp)	X	X	X	X	X	X	X	X	X		X ⁱ
O₂ therapy status and SpO₂	X	X	X	X	X	X	X	X	X	X	X
12-lead ECG	X	X ^a		X ^a		X ^a		X ^a			X ⁱ
Biomarker plasma samples: MIF, IL-1β, IL-6, TNF-α	X ^b	X		X		X		X	X		
PK blood sample^c		X		X		X					
CBC, CMP, CRP, D-dimer, PT, INR	X ^d	X		X		X		X	X		X ⁱ
Randomize^f	X										
Administer study drug		X ^h	X	X	X	X	X	X			
Adverse event review		X	X	X	X	X	X	X	X	X	X
Prior/Concomitant medication review	X	X	X	X	X	X	X	X	X	X	X
Record survival status^j									X	X	X

^a 12-lead ECG to be done between 2-4 hours after AM dose.

^b Biomarker blood sample collection at screening is optional if Screening and Day 1 assessments occur on the same day.

^c Collect PK samples on Day 1 in the AM prior to study drug dosing and at 2, 4, 8, and 12 hours (Predose of PM dose); Day 3 and Day 5 prior to AM study drug dosing. PK samples to be collected for 8 subjects only.

^d Serum β-hCG for pre-menopausal women.

^e Telephone follow-up if subject is not in hospital. If subject is no longer hospitalized or cannot return due to COVID restrictions, a telephone follow-up to record O₂ usage/levels, AEs and conmeds may be conducted. All other assessments are optional.

^f Subjects may be randomized during the Screening Phase after all of the screening assessments are completed and subject is considered eligible for the study or on Day 1.

^g If subject prematurely discontinues from the study or is discharged from the hospital on Days 2, 4, or 6 collect biomarkers samples in addition to other scheduled assessments. If subject prematurely discontinues from the study or is discharged on Days 1, 3, 5, or 7, conduct the study assessments scheduled on those days.

^h The first dose of study drug may be started in the AM or the PM.

ⁱ Vital signs, ECG and safety labs will be done in intubated subjects only.

Survival status is captured on the NIAID questionnaire.

^j Five (5) subjects were consented under Amendment 4.

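### SAP 10.2 tests six Day 60 efficacy endpoints although, by the SAP's own account, about five subjects at most have a Day 60 visit; Day 60 should be descriptive, with a stated denominator

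*Combined protocol and SAP*

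**What the plan says.** SAP 10.2 lists six efficacy endpoints with a Day 60 time point: freedom from respiratory failure, mechanical ventilation or intubation, change in NIAID status, at least one point of NIAID improvement, all-cause mortality, and hospital discharge. The last two read "All-cause mortality at Days 28 and Day 60* Proportion of the subjects discharged from hospital at Day 7, 14, 28 and 60". On method: "All secondary endpoints that are defined as proportion variables will be analyzed using" Pearson's chi-square. The NIAID change goes to ANCOVA with treatment and baseline. Everything is one-sided at 0.025 and unadjusted. SAP 6.1 and SAP 10 place efficacy in the Full Analysis Set, which SAP 6 defines as everyone randomized.

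On who has a Day 60 visit, SAP 3.1 describes "Day 60 (subjects enrolled under amendment 4 only) post-baseline visit". A note under SAP 13.2 states "Five (5) subjects were consented under Amendment 4". SAP 13.1 records 31 consented under Amendment 2, whose schedule has no Day 60 column. SAP 1 adds "No subjects were consented under Protocol v.1.0, Amendment 1, and Amendment 3".

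A footnote narrows this further: "Intubated subjects only on Study Day 60". The protocol differs. Sections 11.3 and 15.3.3 have clinical status, oxygen use and survival assessed at Day 60 in all subjects, and limit only vital signs, ECG and safety laboratory tests to intubated subjects.

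The SAP gives no exact-test fallback, minimum cell count or Day 60 denominator. Its rule that unknown status counts as nonresponse (SAP 10.1) covers only the two co-primary endpoints.

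**The concern.** The SAP specifies large-sample inference at a time point where its own figures leave a handful of subjects. Two things are at stake.

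- With so few people the Pearson approximation can cross the stated threshold when the exact evidence is nowhere near it. Below a certain count it cannot cross at all.
- The Full Analysis Set contains subjects with no Day 60 visit, so whoever programs the tables must choose the denominator, possibly after unblinding. SAP 5 says the results will be used to design later studies, so a Day 60 p-value could carry weight it has not earned.

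**Working it through.** **The plan's own figures.** SAP 7.5 equates one-sided 0.025 with two-sided 0.05. Both give z = 1.960, so the chi-square threshold is 1.960² = 3.84. The planned size of about 40 cannot be reproduced, because SAP 5 gives no inputs for it.

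**How many subjects.** Consented: 31 + 5 = 36, with none under other versions. A Day 60 visit is possible for at most 5, and 5/36 = 13.9%. Consent is not randomization, so 5 is an upper bound if enrolment had closed. If recruitment ran on to 40 under Amendment 4, taking consented as randomized, the bound is 5 + (40 − 36) = 9.

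**Pearson under complete separation.** With all n1 subjects in one arm responding and none of n2 in the other, and N = n1 + n2:

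chi-square = N(n1·n2)² / (n1·n2·n1·n2) = N

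The one-sided p is taken from the signed root, 1 − Φ(√N). The smallest one-sided Fisher p is 1/C(N, n1). The worst-case size is the maximum over a common rate p of the probability of the rejecting table. For 2 v 3 this is p²(1 − p)³ at p = 0.4, which is 0.16 × 0.216 = 0.0346.

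| Split | Chi-square | Pearson p | Fisher p | Worst-case size |
|---|---|---|---|---|
| 1 v 1 | 2 | 0.0786 | 0.50 | 0 |
| 1 v 2 | 3 | 0.0416 | 0.33 | 0 |
| 2 v 2 | 4 | 0.0228 | 0.167 | 6.25% |
| 1 v 3 | 4 | 0.0228 | 0.25 | 10.5% |
| 2 v 3 | 5 | 0.0127 | 0.10 | 3.5% |
| 1 v 4 | 5 | 0.0127 | 0.20 | 8.2% |

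Enumerating every 2×2 table for these splits and their mirror images shows that complete separation is the only table Pearson rejects. The smallest expected counts in the rejecting tables run from 0.2 to 1.0. With the Yates correction the one-sided p-values are 0.096 to 0.253, so none is significant.

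**ANCOVA.** Intercept, treatment and baseline use three parameters, so five subjects leave 5 − 3 = 2 residual degrees of freedom (critical t 4.30).

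**Denominator.** An Amendment 2 subject who died by the last scheduled survival record is known to be dead at Day 60. The Day 60 status of survivors is not collected, so a mortality proportion over the Full Analysis Set needs an imputation rule, and none is stated.

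The choice matters for the proportion endpoints too. Assume 18 per arm and count every unknown as a nonresponder. Then 4/18 v 0/18 gives Pearson p = 0.017 (Fisher 0.052), and 5/18 v 0/18 gives 0.0080 (Fisher 0.023). If only the five Amendment 4 subjects can be responders, those tables need four or all five of them in one arm. The result would then partly reflect how those five were allocated.

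**The case against.** The strongest reply is that the SAP as written rarely lets the false positive happen. Every Day 60 efficacy endpoint carries the intubated-only footnote, so four or five analysed subjects would require at least four of the five Amendment 4 subjects to have been intubated, and the arms would then have to separate completely. This stands. A reader might infer that the plan will produce spurious Day 60 significance; the documents support only that it could. With three or fewer subjects the fault is the opposite one: the test cannot reject.

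Second, a reader might infer that none of the six tests could be valid. The Fisher and Pearson argument covers the five proportion endpoints only. ANCOVA on 2 residual degrees of freedom holds its size under its normal-error model. It is uninformative, and nothing here shows it to be invalid.

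Third, the documents never say that enrolment had closed. The past tense in SAP 3.3, 13.1 and 13.2 favours closure, but about 40 is still the plan. With nine subjects split 4 v 5 the smallest Fisher p is 1/126 = 0.008, so an exact test could reach 0.025. The denominator gap would remain.

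Fourth, the SAP does not say that Day 60 mortality uses all 36. SAP 3.1 and the footnote point to a smaller group, and the general Full Analysis Set rule sits against them. That is a conflict to resolve; it is not an instruction to count everyone.

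Finally, success rests on the Day 7 co-primary endpoints, and the secondary tests are openly unadjusted. That limits the importance of the point but does not make the tests useful.

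**Conclusion.** The point holds. SAP 10.2 plans six one-sided 0.025 tests at Day 60, where the SAP's own counts give at most five subjects if enrolment had closed. The intubated-only footnote makes the number smaller and conflicts with the protocol, so the two must be reconciled; lifting the footnote would still leave the cap at five.

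With five or fewer subjects, the five proportion tests cannot be both valid and significant. The best exact p is 0.10, and where Pearson can reject at all its worst-case size is 3.5% to 10.5% against a nominal 2.5%. The ANCOVA is uninformative. The Full Analysis Set does not fit Day 60 mortality as the visits were designed.

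The conclusion assumes closed enrolment and uncorrected Pearson with a signed-root one-sided p-value. It concerns secondary endpoints only.

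A reader might go on to infer that Day 28 should be declared the last between-arm comparison for every endpoint. The documents do not support that. In the Amendment 2 schedule (SAP 13.1), NIAID status has ten marks and oxygen status nine, so oxygen status appears not to have been scheduled at the last follow-up. That column's heading is lost in the text available, so Day 28 is itself an inference.

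**What to change.** - Keep Day 60 in the objectives (SAP 2.1.2), since protocol 10.2 and 19.3 carry Day 60 secondary objectives and endpoints.
- In SAP 2.2.2, SAP 10.2 and Tables 14.2.3 to 14.2.8, make Day 60 descriptive only: counts by arm and a by-subject listing, with no p-values. Listings of NIAID status, oxygen use, discharge and survival are already planned in SAP 13.4.
- State the Day 60 denominator: Amendment 4 subjects with a Day 60 assessment, with an earlier death counted as known status.
- Reconcile the intubated-only footnote (SAP 2.1.2, 2.2.2, 7.8 and 10.2) with protocol 11.3 and 15.3.3, and state whether enrolment had closed.
- Before naming a last inferential time point, check endpoint by endpoint what was scheduled at Day 28 under Amendment 2.

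The cost is SAP wording and table shells, plus six nominal secondary p-values. No data are lost, and the Day 7 co-primary conclusions do not change.

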3.3 Method of Treatment Assignment and Randomization

During the Double-blind Treatment Phase, randomization occurred in a 1:1 ratio (MN-166: Placebo). The randomization scheme was generated by an independent statistician and sent to each site's unblinded pharmacist in a password protected file.

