10.1 Primary Efficacy Variable Analysis

The co-primary efficacy endpoints are listed below. The primary analysis for each of these two endpoints will be conducted using Pearson's chi-square tests. Because study success is defined as success on both, each of the two co-primary endpoints will be tested using a one-sided significance level of 0.025.

- Proportion of subjects free from respiratory failure
 - Calculate the proportion of the subjects free from supplemental oxygen (invasive mechanical ventilation, non-invasive ventilation, high-flow oxygen, ECMO, CPAP, BiPAP, nasal cannula) at Day 7
- Proportion of subjects with improvement in clinical status using the NIAID 8-point ordinal scale and discharge record at Day 7
 - Calculate the proportion of the subjects who improved at least one-point from baseline

For each of the two co-primary endpoints, subjects whose response status is unknown will be assumed to be nonresponders.

A supportive analysis for each of the two co-primary endpoints will be conducted using the Mantel-Haenszel test stratified by the randomization stratification variable (use of IL-6 antibody therapy).

Confidential

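### Pearson's chi-square does not hold the stated one-sided 0.025 level at about 18 per arm, and at Day 60 it would be run on at most five people

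*Combined protocol and SAP*

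**What the plan says.** SAP 10.1, on the co-primary endpoints: "The primary analysis for each of these two endpoints will be conducted using Pearson's chi-square tests". The level follows in the same section: "each of the two co-primary endpoints will be tested using a one-sided significance level of 0.025".

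SAP 10.2, on the secondary endpoints: "All secondary endpoints that are defined as proportion variables will be analyzed using" Pearson's chi-square. This covers freedom from respiratory failure, ventilation, NIAID improvement, mortality and discharge. On the level it says: "All secondary analyses will be conducted using one-sided tests at the alpha=0.025 level of significance, with no adjustments for multiplicity".

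Neither section gives a continuity correction, an exact test or a minimum expected count. The only other test of proportions is a supportive Mantel-Haenszel test, stratified by IL-6 antibody use, for the co-primaries alone.

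On numbers, SAP 3.1 says "Approximately 40 participants are planned to be enrolled", allocated 1:1. Appendix 13.1 records 31 subjects consented under Amendment 2, and Appendix 13.2 adds: "Five (5) subjects were consented under Amendment 4". SAP 3.1 limits the Day 60 visit to Amendment 4 subjects, and the footnote in SAP 10.2 limits Day 60 analyses to intubated subjects.

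**The concern.** Pearson's chi-square takes its critical value from a large-sample approximation. With fewer than 20 subjects per arm, its true level depends on the underlying rate and the arm split, and need not equal 0.025. If it runs above 0.025, the SAP states a property that the test does not have. This affects the two tests that decide study success and every secondary proportion.

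At Day 60 the denominator is so small that a p-value below 0.025 can come from four people. Printed beside the other secondary results, such a value would be read as evidence.

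**Working it through.** **Inputs.** Test and level are from SAP 10.1 and 10.2. Arm sizes are 20/20 (planned) and 18/18, 17/19 or 16/20 for 31 + 5 = 36 consented. The two uneven splits are assumptions. SAP 5 gives no expected rates, so the common null rate π is scanned over its whole range. The number intubated is not given, so Day 60 splits are illustrative.

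**Test.** With x1 of n1 and x2 of n2 responders and pooled proportion p,

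z = (x1/n1 − x2/n2) / √[p(1 − p)(1/n1 + 1/n2)].

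z² is the Pearson statistic. One-sided 0.025 means rejecting when z ≥ 1.960.

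**The plan's figure.** 0.025 is the normal tail area beyond 1.960. The exact size is

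size(π) = Σ Bin(x1; n1, π) · Bin(x2; n2, π), summed over all tables with z ≥ 1.960.

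| Arms | Maximum size, chi-square | Share of π with size above 0.025 | Maximum size, Boschloo |
|---|---|---|---|
| 20/20 | 0.0267 | 42% | 0.0232 |
| 18/18 | 0.0326 | 40% | 0.0238 |
| 17/19 | 0.0349 | 47% | 0.0249 |
| 16/20 | 0.0335 | 25% | 0.0238 |

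At 18/18 the size by rate is 0.0044 at 5%, 0.0167 at 10%, 0.0230 at 15%, 0.0301 at 40% and 60%, and 0.0326 at 50%. The excess runs from about 30% to 70%.

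A table in that range: 12/18 against 6/18 has p = 0.5, so z = 0.333 / √(0.25 × 2/18) = 0.333/0.167 = 2.0 and one-sided p = 0.023. Boschloo's test gives 0.033. The tables 11 vs 5 and 13 vs 7 also change verdict.

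**Day 60.** At most five people are available. In each split below, only one table rejects in the stated direction.

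- 2/2: the table 2/2 vs 0/2 has p = 0.5 and z = 1/√(0.25 × 1) = 2.0, one-sided p = 0.023. Size = π²(1 − π)², which at π = 0.5 is 0.0625.
- 2/3: the table 2/2 vs 0/3. Size = π²(1 − π)³, which at π = 0.4 is 0.16 × 0.216 = 0.035.
- 1/4: the table 1/1 vs 0/4. Size = π(1 − π)⁴, which at π = 0.2 is 0.2 × 0.4096 = 0.082.
- 1/3: the table 1/1 vs 0/3. Size = π(1 − π)³, which at π = 0.25 is 0.25 × 0.4219 = 0.106.

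The smallest one-sided Fisher p-value possible with five or fewer subjects is 1/C(5,2) = 0.10.

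**Power** (rates assumed for illustration):

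| Rates and arms (active/placebo) | Chi-square | Boschloo | Fisher |
|---|---|---|---|
| 80% vs 50%, 18/18 | 0.50 | 0.47 | 0.36 |
| 70% vs 40%, 18/18 | 0.49 | 0.41 | 0.36 |
| 70% vs 40%, 19/17 | 0.51 | 0.41 | 0.37 |

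**The case against.** This is a pilot with no power calculation, and its results are meant to inform later studies. Success requires both co-primaries, which lowers the joint error, and the secondary tests are openly unadjusted. At the planned 20/20 the excess is at most 0.17 percentage points. At 18/18 it is under one point and covers about 40% of null rates. An exact test is not free either: 70% vs 40% at 18/18 loses 8.5 points of power. All of this stands, and it keeps the general point small. It does not make the stated level correct, and part of the lost power exists only because the chi-square exceeds that level. The Mantel-Haenszel analysis does not help, since it is also a large-sample method.

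A reader might infer more: that the test wrongly declares significance on rare-event tables such as 4/18 vs 0/18, where expected event counts are 2. That is not supported. One-sided p-values for that table are 0.017 by chi-square, 0.033 by Boschloo and 0.019 by Barnard, so a valid unconditional exact test agrees with the chi-square. With balanced arms of 18, the chi-square is also conservative at rates of 10% or less. An uneven split can reverse this in one direction (0.031 at 10% for 16/20), but nothing in the documents says that split occurred.

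It can also be said that Day 60 is a denominator problem that no choice of test repairs. That is right, and is why the remedy there is to list the data.

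**Conclusion.** The point holds in two parts of unequal weight.

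The Day 60 rule is unsound as written. A chi-square on at most five people can declare significance from two responders against none in four subjects, with a maximum size up to 0.106 at 1/3. It is not inflated at every split (0.035 at 2/3), but no split allows a useful test. The ceiling of five follows from the Amendment 4 restriction alone; limiting the analysis to intubated subjects can only reduce it.

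For the other proportions, the stated 0.025 is approximate. The true level can reach about 3.3% to 3.5% with 36 subjects and 2.7% with 40. This is a modest misstatement of a nominal level in a pilot, and it does not show that any particular result would be wrong.

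Assumptions: chi-square means the uncorrected statistic, which is the plain reading; 36 is the number consented, so the number randomized may be lower; arm splits, response rates and the intubated count are not in the documents.

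**What to change.** 1. In SAP 10.2, state that Day 60 proportions in intubated subjects will be listed and not tested. Remove Day 60 from Tables 14.2.3, 14.2.4 and 14.2.6 to 14.2.8. Listings 16.2.6.1 to 16.2.6.4 already cover the underlying data. There is essentially no cost.

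2. In SAP 10.1 and 10.2, name one unconditional exact test, Boschloo's, for the other unstratified proportions. Its maximum size is 2.3% to 2.5% at the arm sizes checked. Offering a choice between Boschloo and Barnard would leave the test open, because the two can disagree on the same table. The cost is about 0 to 11 points of power, depending on rates and arm split. If that is not acceptable, keep Pearson's chi-square and state that its one-sided level is approximate and can reach about 3.5%.

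Both are wording changes that need no new data. Make them before unblinding.

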15.3.4 Early Termination/Discharged from Hospital

If subject is no longer hospitalized or cannot return due to COVID restrictions, a telephone follow-up to record O₂ usage, AEs and conmeds taken will be conducted. All other assessments are optional.

If subject terminates early from the study or is discharged from the hospital prior to completion of the Treatment Phase, complete assessments scheduled for that Study Day. If subject discontinues or are discharged on Days 2, 4, or 6, collect a biomarker sample in addition to their regularly scheduled assessments.

Subjects who are discharged prior to Day 7, will be given their study medication to be taken at home and a pulse oximeter (ClinicalGuard CMS-50DL Fingertip Pulse Oximeter) supplied by the sponsor to record their O₂ saturation once daily until Day 14.

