6 ANALYSIS POPULATIONS

The following analysis populations are planned for the studies:

- **Full Analysis Set (FAS)** will include all randomized subjects.
- **Safety Analysis Set (SAS)** will include all randomized subjects who received at least one dose of study drug and had at least one post-dose safety assessment.
- **Per Protocol Analysis (PP):** will consist of the FAS subjects excluding those with major protocol violations.

Confidential

- **Pharmacokinetic Population (PK):** will consist of the subjects for which PK collection was performed. Eight subjects are anticipated to participate in PK sample collection.

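### The by-visit biomarker ANCOVA has no rule for discharged or deceased subjects and no place for the Day 2, 4 or 6 discharge sample, so the Day 7 and Day 14 comparisons may rest mainly on subjects still in hospital

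*Combined protocol and SAP*

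**What the plan says.** **Endpoint and model.** SAP 10.2 lists change from baseline in MIF, IL-1β, IL-6, TNF-α "and C-reactive protein (CRP) at Day 3, 5, 7 and 14". The method is: "Secondary endpoints that are defined as the change from baseline will be analyzed using analysis of covariance (ANCOVA) models", with treatment as factor and the baseline value as covariate. On error control: "All secondary analyses will be conducted using one-sided tests at the alpha=0.025 level of significance, with no adjustments for multiplicity". Protocol 19.3 names Day 7 only for this endpoint.

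**Population and missing data.** Under SAP 6 the Full Analysis Set "will include all randomized subjects". Protocol 19.0 leaves the handling of missing data and deaths to the SAP. The SAP's only such rule for efficacy is in 10.1: "For each of the two co-primary endpoints, subjects whose response status is unknown will be assumed to be nonresponders". Nothing equivalent covers the biomarkers.

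**Sampling after discharge.** Protocol 15.3.4 provides a telephone contact for oxygen use, adverse events and medications, and adds: "All other assessments are optional". Footnote e of protocol Table 1 and section 15.3.3 (Day 14) agree. Section 11.3 lists the Day 14 biomarkers for subjects still hospitalised. The Amendment 2 schedule in SAP 13.1 has the same rule.

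**Sampling at discharge.** Protocol 15.3.4 requires an extra sample: "If subject discontinues or are discharged on Days 2, 4, or 6, collect a biomarker sample". On Days 1, 3, 5 and 7 the sample scheduled for that day is taken (section 11.4, Table 1 footnote g).

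**Visit windows.** SAP 7.3 gives Days 2 to 7 a window of zero days and Day 14 a window of ±3 days.

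**Discharge as an outcome.** SAP 2.2.2 includes "Proportion of the subjects discharged from hospital at Days 7, 14, 28 and 60" among the secondary endpoints, and the discharge record enters the second co-primary endpoint.

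**The concern.** An ANCOVA of change at Day 7 uses only subjects with a Day 7 value. Subjects who went home earlier need not have one, even though protocol 11.4 has them finish study drug at home. Those who died before Day 7 cannot have one. Whether a subject enters the comparison therefore depends on recovery or death, both of which treatment may affect.

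If ibudilast speeds recovery, more of its subjects leave early, and those left to be sampled are its slower responders. The two sampled groups are then no longer comparable by randomisation. The natural direction is dilution of a real anti-inflammatory effect, with fewer subjects to detect it.

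The protocol provides for part of this by requiring a sample on discharge on Days 2, 4 and 6, but the SAP gives that sample no use. A trial meant to inform later studies could discard data it has collected and under-read its own mechanism result.

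**Working it through.** The plan states no power, discharge rate or missing-data rate for the biomarkers, so there is no figure of its own to reproduce. The check has two parts.

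**1. Which samples reach the ANCOVA**

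| Subject's course | Sample under the protocol | Enters Day 7 ANCOVA? |
|---|---|---|
| In hospital through Day 7, or discharged on Day 7 | Scheduled Day 7 sample | Yes |
| Discharged on Day 3 or 5 | That day's scheduled sample; later draws optional | Only if an optional Day 7 draw is made; otherwise Day 3 or 5 analysis only |
| Discharged on Day 2, 4 or 6 | Extra sample; later draws optional | Only if an optional Day 7 draw is made; the extra sample has no visit (zero-day window) |
| Died before Day 7 | No Day 7 sample | No; no rule stated |

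Day 14 follows the same pattern, except that its window admits Days 11 to 17.

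**2. Size, by illustration**

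From the documents: about 40 subjects planned, 1:1 (SAP 3.3, 5); 31 + 5 = 36 consented (SAP 13.1, 13.2), which need not equal the number randomised; one-sided α 0.025. Assumed, because the documents are silent: discharge before Day 7 of 30 to 70%, SD 1, correlation ρ of 0.3 to 0.6 between biomarker fall and readiness for discharge, and no optional draws made.

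*Precision.* The difference detectable with 80% power is (1.960 + 0.842) × √(2/n), with n per arm.

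| Discharged, both arms | N = 40 | N = 36 |
|---|---|---|
| 0% | n = 20: 0.89 SD | n = 18: 0.93 SD |
| 30% | n = 14: 1.06 SD | n = 12.6: 1.12 SD |
| 50% | n = 10: 1.25 SD | n = 9: 1.32 SD |
| 70% | n = 6: 1.62 SD | n = 5.4: 1.70 SD |

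*Bias.* Let the drug change the Day 7 biomarker by τ, and let a subject be discharged when a standard normal index exceeds c. In the drug arm the index is shifted by m = γ − ρτ, where γ is any effect on discharge by another route. With λ(a) = φ(a)/Φ(a), the expected difference among those sampled is τ + ρ[λ(c − m) − λ(c)].

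| τ | γ | ρ | Discharged, placebo / drug | Calculation | Expected difference |
|---|---|---|---|---|---|
| −0.8 | 0 | 0.3 | 30% / 39% | −0.8 + 0.3(0.626 − 0.497) | −0.76 |
| −0.8 | 0 | 0.6 | 30% / 48% | −0.8 + 0.6(0.770 − 0.497) | −0.64 |
| −0.8 | 0 | 0.6 | 50% / 68% | −0.8 + 0.6(1.126 − 0.798) | −0.60 |
| −0.8 | 0.5 | 0.6 | 30% / 68% | −0.8 + 0.6(1.109 − 0.497) | −0.43 |
| −0.8 | 0.8 | 0.6 | 50% / 90% | −0.8 + 0.6(1.754 − 0.798) | −0.23 |
| 0 | 0.5 | 0.6 | 30% / 49% | 0 + 0.6(0.782 − 0.497) | +0.17 |

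Simulation (4000 trials, 20 per arm, ANCOVA on sampled subjects) agrees: −0.76, −0.64, −0.60, −0.43, −0.23 and +0.18. Power in the five rows with an effect is 0.46, 0.38, 0.22, 0.15 and 0.04. It would be about 0.65 to 0.67 if a discharge sample stood in for the missing Day 7 value with little noise, which is optimistic. With no effect on either biomarker or discharge there is no bias (one-sided rejection 0.024 to 0.029).

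**The case against.** **The SAP does not restrict the analysis to inpatients.** Correct. A reader might infer that Day 7 and Day 14 are compared only in hospitalised subjects. The documents do not say so: later draws are optional, not barred, and discharge on Day 7 yields a Day 7 sample. What they support is that the comparison may rest mainly on inpatients.

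**Discharge samples are not all unused.** Correct. Discharge on Day 3, 5 or 7 produces a scheduled sample that enters that day's ANCOVA. The gap concerns Days 2, 4 and 6.

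**Days 7 and 14 are not the only test of mechanism.** Correct. Days 3 and 5 are tested too. Day 3 is probably least affected and Day 5 less affected than Day 7.

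**The loss may be small.** This cannot be excluded. A reader might take it that most of the effect disappears. If the drug acts on the biomarker wholly through the same score that decides discharge, the calculation does retain only 0.129/0.4 = 32% or 0.231/0.8 = 29% at 50% placebo discharge. With 18 per arm, a shift of 0.8 SD and correlation 0.9, simulated power drops from about 55% to 5%. That is a severe model. Where the drug acts on the biomarker directly, −0.76/−0.80 = 95% to −0.60/−0.80 = 75% is retained unless it also speeds discharge by another route.

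**Sign reversal.** In these illustrations, a drug that truly lowers the biomarker still has an estimate in its favour. The average difference goes against the drug only where it hastens discharge with no biomarker effect. One-sided rejection there is about 0.01, so the risk is a missed signal and not a false claim.

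**A last-available-sample endpoint is no clean cure.** This stands. Sampling day would itself depend on discharge. If the drug arm is sampled 0.6 to 0.7 days earlier and levels fall naturally by 0.1 to 0.2 SD a day, that arm looks 0.6 × 0.1 = 0.06 to 0.7 × 0.2 = 0.14 SD worse with no true difference. A Day 2 sample may also precede steady state, which protocol 9.3 puts at within 3 days.

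**Conclusion.** The concern holds as stated in the heading. Optional draws after discharge, no missing-data or death rule, and a required sample with no analysis visit together make the Day 7 and Day 14 comparisons, and to a lesser degree Day 5, conditional on an outcome that the trial itself tests. Following the SAP exactly also discards data the protocol collects, so this is more than missing detail.

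The likely direction is attenuation plus lost precision. The size cannot be found from the documents. For a true −0.80 SD, the illustrations run from slight (−0.76) to severe (−0.23), and at N = 36 the detectable difference rises from 0.93 to 1.32 SD if half are discharged. These figures rest on assumed discharge rates, correlations and SD, and on nobody returning for an optional draw. The bias requires that discharge relate to the biomarker and differ by arm. The loss of precision requires neither.

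The endpoint is secondary and unadjusted, in a pilot without a power calculation. The change is worth making because it is cheap, not because a main conclusion depends on it.

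**What to change.** In SAP 10.2:

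1. Analyse each biomarker in the Full Analysis Set with a baseline-adjusted repeated-measures mixed model that uses every collected sample at its actual study day, including the Day 2, 4 and 6 discharge samples. State how death is handled.
2. Keep Day 3 as the scheduled comparison least affected by discharge.
3. Show the Day 7 and Day 14 by-visit results with n per arm, labelled as subjects with a sample, mainly still hospitalised, and not read as a randomised comparison. Label the Day 7 and Day 14 laboratory changes the same way.
4. A change to the last on-treatment sample may be added as supportive only, with sampling day tabulated by arm.
5. Add a biomarker table to SAP 13.3, which lists none. Confirm whether the Day 2, 4 and 6 sample includes CRP: protocol 14.3 counts it as a biomarker, but Table 1 places it in the laboratory row.

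The mixed model is preferred on one illustrative simulation in which the effect builds over days (true difference −0.60). It returned about −0.60 to −0.62, against −0.50 to −0.58 for the Day 7 ANCOVA and −0.23 to −0.40 for the last-sample endpoint.

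Cost: SAP wording and slightly more modelling; no new samples. The model relies on values being missing at random given the observed samples. That cannot be verified and should be stated.
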